9.5 DISSEMINATION OF DATA AND PROTECTION OF TRADE SECRETS

Regardless of the outcome of a trial, the Sponsor is dedicated to openly providing information on the trial to healthcare professionals and to the public, at scientific congresses, in clinical trial registries, and in peer-reviewed journals. The Sponsor will comply with all requirements for publication of study results. Study data may be shared with others who are not participating in this study (see Section 8.4 for details), and redacted Clinical Study Reports and/or other summaries of clinical study results may be available in health authority databases for public access, as required by local regulation, and will be made available upon request. For more information, refer to the Roche Global Policy on Sharing of Clinical Study Information at the following website:

<https://www.roche.com/innovation/process/clinical-trials/data-sharing/>

The results of this study may be published or presented at scientific congresses. For all clinical trials in patients involving an IMP for which a marketing authorization application has been filed or approved in any country, the Sponsor aims to submit a journal manuscript reporting primary clinical trial results within 6 months after the availability of the respective Clinical Study Report. In addition, for all clinical trials in patients involving an IMP for which a marketing authorization application has been filed or approved in any country, the Sponsor aims to publish results from analyses of additional endpoints and exploratory data that are clinically meaningful and statistically sound.

The investigator must agree to submit all manuscripts or abstracts to the Sponsor prior to submission for publication or presentation. This allows the Sponsor to protect proprietary information and to provide comments based on information from other studies that may not yet be available to the investigator.

In accordance with standard editorial and ethical practice, the Sponsor will generally support publication of multicenter trials only in their entirety and not as individual center data. In this case, a coordinating investigator will be designated by mutual agreement.

Authorship will be determined by mutual agreement and in line with International Committee of Medical Journal Editors authorship requirements. Any formal publication of the study in which contribution of Sponsor personnel exceeded that of conventional monitoring will be considered as a joint publication by the investigator and the appropriate Sponsor personnel.

Any inventions and resulting patents, improvements, and/or know-how originating from the use of data from this study will become and remain the exclusive and unburdened property of the Sponsor, except where agreed otherwise.

9.6 PROTOCOL AMENDMENTS

Any protocol amendments will be prepared by the Sponsor. Protocol amendments will be submitted to the IRB/EC and to regulatory authorities in accordance with local regulatory requirements.

Approval must be obtained from the IRB/EC and regulatory authorities (as locally required) before implementation of any changes, except for changes necessary to eliminate an immediate hazard to patients or changes that involve logistical or administrative aspects only (e.g., change in Medical Monitor or contact information).

Appendix 1: Schedule of Activities for Part A and Part B

	Scr. ^a	Rand. ^a	Treatment Period 1			WP	Pretreat.	Treatment Period 2			WP	SFU ^b	UV ^c	TD ^d
Study Visit	1	2	3	4			5	6	7		8			
Study Day	-21 to -1													
Vitamin K-dependent coagulation factors			X		X			X		X		X	X	X
Viral serology	X													
FSH (if necessary) ^j	X													
Pregnancy test ^k	X		X					X				X	X	
COVID-19 testing (if necessary) ⁿ	X													
Chest X-ray (if no historical Chest X-ray or HRCT) ^o	X													
VAS ^q	X ^r		Daily ^r				Daily ^r					X		X
NRS	X ^r		Daily ^r				Daily ^r					X		X
FeNO			X		X			X		X				
Pre-bronchodilator spirometry ^s	X		X		X		X	X		X				

Appendix 1: Schedule of Activities for Part A and Part B

	Scr. ^a	Rand. ^a	Treatment Period 1			WP	Pretreat.	Treatment Period 2			WP	SFU ^b	UV ^c	TD ^d
Study Visit	1		2	3	4			5	6	7		8		
Study Day	-21 to -1													
Mannitol challenge test ^t	x				x (Optional)					x (Optional)				
Post-bronchodilator spirometry ^s	x ^u													
24-hour OCC (VitaloJAK [®]) ^v	x ^w	x ^x	x ^y		x ^y		x ^x	x ^y		x ^y				
Randomization		x												
Study drug administration (GDC-6599 or placebo)			■ on Days 1–14 ^{aa}					■ on Days 30–43 ^{aa}						
Patient-reported daily compliance eDiary			Daily					Daily						

Appendix 1: Schedule of Activities for Part A and Part B

[figure not shown]
	Scr. ^a	Rand. ^a	Treatment Period 1			WP	Pretreat.	Treatment Period 2			WP	SFU ^b	UV ^c	TD ^d
Study Visit	1		2	3	4			5	6	7		8		
Study Day	-21 to -1													
Concomitant medications	x	x	x	x	x		x	x	x	x		x	x	x
Adverse events ^{dd}	x	x	x	x	x		x	x	x	x		x	x	x

ATS =American Thoracic Society; COPD =chronic obstructive pulmonary disease; COVID-19=coronavirus disease 2019; CRC=chronic refractory cough; eDiary=electronic diary; ERS =European Respiratory Society; FeNO=fractional exhaled nitric oxide; FEV₁=forced expiratory volume in 1 second; FSH=follicle-stimulating hormone; FVC =forced vital capacity; HBsAg=hepatitis B surface antigen; HCV=hepatitis C virus; HRCT=high-resolution computed tomography; NRS=Numeric Response Scale; OCC=objective cough count; PK=pharmacokinetic; Pretreat.=pretreatment; PRO=patient-reported outcome; Rand.=randomization; RAST =radioallergosorbent test; RBR=Research Biosample Repository; Scr.=screening; SFU=safety follow-up; TD=treatment discontinuation; ULN=upper limit of normal; UCC=unexplained chronic cough; UV=unscheduled visit; VAS=visual analog scale; WES=whole exome sequencing; WGS=whole genome sequencing; WP=washout period .

Notes: On days *with in-clinic dosing*, all assessments should be performed prior to *study drug administration*, unless otherwise specified.

Appendix 1: Schedule of Activities for Part A and Part B

- ^a Results of standard-of-care assessments performed prior to obtaining informed consent and within 21 days prior to Day 1 may be used; such assessments do not need to be repeated for screening. Patients who do not meet the criteria for participation in this study may qualify for one re-screening opportunity (for a total of two screenings per patient) at the investigator's discretion, as described in Section 3.1.1. If a patient has completed all screening assessments and is eligible to enroll, randomization of the patient may begin as soon as 7 days into the screening period. *The screening visit may occur during a single day or over a maximum of 3 days. If performed during a single screening visit, use of the VitaloJAK cough recorder should start at least 30 minutes after the mannitol challenge test.*
- ^b Patients who complete both treatment periods will return to the clinic for a safety follow-up visit (Study Visit 8) at [REDACTED].
- ^c Visit not specified by the protocol. Assessments (possibly including PK and biomarker sample collection; see [REDACTED] should be performed as clinically indicated. Suggested safety assessments are outlined in this appendix table.
- ^d Patients who discontinue study drug prematurely will return to the clinic for a treatment discontinuation [REDACTED] days after their final dose of study drug.

- ^g Informed consent must be documented before any study-specific screening procedure is performed and may be obtained more than 21 days before initiation of study treatment.
- ^h Chemistry panel limited to liver function tests (ALP, ALT, AST, total and direct bilirubin). If finding of an elevated ALT/AST ($>3 \times$ ULN and $<5 \times$ ULN) and no other findings consistent with Hy's Law are observed, continue study drug and return to clinic for and unscheduled visit to repeat liver function tests (ALT, AST, GGT, alkaline phosphatase, total and direct bilirubin) within 48 hours. If finding of an elevated ALT/AST $\geq 5 \times$ ULN in isolation or $>3 \times$ ULN in combination with other findings consistent with Hy's Law are observed, discontinue study drug, repeat liver function test within 72 hours, assess patient for signs/symptoms of hepatic failure, assess for other causes of liver dysfunction (e.g., viral hepatitis, concomitant medications, etc.), and continue to monitor liver function tests until abnormalities resolve (see Section 5.1.3.2).
- For patients at participating sites who have provided written informed consent to participate in mobile nursing visits, these assessments may be performed by a trained nursing professional at the patient's home or another suitable location, if mobile nursing is available.
- ⁱ The ImmunoCAP Specific IgE test panel, skin prick test, or RAST is required **only for patients with asthma who do not have confirmed atopic versus non-atopic status in their medical records**. Patient eligibility may be determined by medical history alone (see Section 4.1.1.2).

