1.2 BACKGROUND ON GDC-6599

GDC-6599 is a small molecule inhibitor of the TRPA1 channel that is under development as a potential oral therapy for the treatment of patients with CRC with asthma or UCC.

[REDACTED]

GDC-6599, administered orally (PO), was well tolerated in both rats and cynomolgus monkeys at doses up to 50 mg/kg/day for 4 weeks. The most significant GDC-6599-related finding was a dose-dependent, reversible prolongation of the coagulation parameters aPTT and PT in both rats and monkeys.

[REDACTED]

GDC-6599 *has been investigated in a completed Phase Ia/b single ascending dose (SAD) and multiple ascending dose (MAD) study (GA43010) in approximately 81 healthy volunteers to explore safety, and the pharmacokinetic and pharmacodynamic profile of the agent. Pharmacodynamic target (TRPA1) inhibition *has been evaluated* using the AITC dermal challenge model (Joseph et al. 2021). No significant clinical, laboratory, or ECG findings have been observed in the initial six dosing cohorts of the SAD portion and three cohorts of the MAD portion of Study GA43010. Based upon the available clinical data, the clinical dose for the current Phase IIa protocol (GA43590) is [REDACTED] (█; see Section 3.3.2). No prior clinical experience with GDC-6599 exists in patients.*

Refer to the GDC-6599 Investigator's Brochure for details on nonclinical and clinical studies.

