5.1.3.2 Management Guidelines

Guidelines for management of specific adverse events are outlined in [Table 4](#).

Additional guidelines are provided in the subsections below. These guidelines are intended to inform rather than supersede an investigator's clinical judgment and assessment of the benefit–risk balance when managing individual cases.

Table 4 Guidelines for Management of Patients Who Experience Adverse Events

Event	Action to Be Taken
Coagulation abnormalities	
Grade ≥ 3 PT prolongation (PT $\geq 1.5 \times$ ULN)	
Discontinue study drug.
INR of > 2 and < 4	
Administer Vitamin K (2.5 mg PO $\times 1$).Repeat coagulation parameters daily until INR improves to < 1.5.

Table 4 Guidelines for Management of Patients Who Experience Adverse Events (cont.)

Event	Action to Be Taken
Coagulation abnormalities	
INR ≥ 4 without evidence of bleeding	
 • Contact Medical Monitor. • Administer Vitamin K (10 mg PO daily) until INR < 1.5 and at least 5 GDC-6599 drug-elimination half-lives have elapsed (estimated to be 4 days). • If no response to Vitamin K, consider administering PCC or FFP. • Consider subspecialist (hematology) consultation.
INR ≥ 4 and Grade 3 or Grade 4 bleeding	
 • Discontinue study drug. • Administer 4-factor PCC or FFP.
Impaired cough reflex	

FFP=fresh frozen plasma; GGT= gamma-glutamyl transferase; IDSA=Infectious Diseases Society of America; PCC=prothrombin complex concentrate; ULN=upper limit normal; PO=by mouth.

^a https://www.idsociety.org/practice-guideline/practice-guidelines/#/date_na_dt/DESC/0/+/.

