Platelets, decreased	100,000 to $<125,000$ cells/mm ³ (100.000×10^9 to $<125.000 \times 10^9$ cells/L)	50,000 to $<100,000$ cells/mm ³ (50.000×10^9 to $<100.000 \times 10^9$ cells/L)	25,000 to $<50,000$ cells/mm ³ (25.000×10^9 to $<50.000 \times 10^9$ cells/L)	$<25,000$ cells/mm ³ ($<25.000 \times 10^9$ cells/L)
PT, high (not on anticoagulation therapy)	1.1 to $<1.25 \times$ ULN	1.25 to $<1.50 \times$ ULN	1.50 to $<3.00 \times$ ULN	$\geq 3.00 \times$ ULN
WBC, decreased: > 7 days of age	2000 to 2499 cells/mm ³ (2.000×10^9 to 2.499×10^9 cells/L)	1500 to 1999 cells/mm ³ (1.500×10^9 to 1.999×10^9 cells/L)	1000 to 1499 cells/mm ³ (1.000×10^9 to 1.499×10^9 cells/L)	<1000 cells/mm ³ ($<1.000 \times 10^9$ cells/L)
WBC, decreased: ≤ 7 days of age	5500 to 6999 (5.500×10^9 to 6.999×10^9 cells/L)	4000 to 5499 (4.000×10^9 to 5.499×10^9 cells/L)	2500 to 3999 (2.500×10^9 to 3.999×10^9 cells/L)	<2500 ($<2.500 \times 10^9$ cells/L)

ULN = upper limit of normal.

Appendix 10: Division of AIDS (DAIDS) Table for Grading the Severity of Adult and Pediatric Adverse Events

Table 1 Severity Grading for Adult and Pediatric Adverse Events (cont.)

Parameter	Grade 1 (Mild)	Grade 2 (Moderate)	Grade 3 (Severe)	Grade 4 (Potentially Life-Threatening)
Urinalysis				
Glycosuria (random collection tested by dipstick)	Trace to 1+ or ≤ 250 mg	2+ or > 250 to ≤ 500 mg	$> 2+$ or > 500 mg	—
Hematuria (not to be reported based on dipstick findings or on blood believed to be of menstrual origin)	6 to < 10 RBCs per high power field	≥ 10 RBCs per high power field	Gross, with or without clots or with RBC casts or intervention indicated	Life-threatening consequences
Proteinuria (random collection tested by dipstick)	1+	2+	3+ or higher	—

Appendix 10: Division of AIDS (DAIDS) Table for Grading the Severity of Adult and Pediatric Adverse Events

Table 7 Severity Grading for Elevated Total Bilirubin in Neonates

Parameter	Grade 1 (Mild)	Grade 2 (Moderate)	Grade 3 (Severe)	Grade 4 (Potentially Life-Threatening)
Neonates ≥ 35 Weeks Gestational Age				
<24 hours of age	4 to < 7 mg/dL (68.4 to < 119.7 µmol/L)	7 to < 10 mg/dL (119.7 to < 171 µmol/L)	10 to < 17 mg/dL (171 to < 290.7 µmol/L)	≥ 17 mg/dL (≥ 290.7 µmol/L)
24 to < 48 hours of age	5 to < 8 mg/dL (85.5 to < 136.8 µmol/L)	8 to < 12 mg/dL (136.8 to < 205.2 µmol/L)	12 to < 19 mg/dL (205.2 to < 324.9 µmol/L)	≥ 19 mg/dL (≥ 324.9 µmol/L)

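### A cheap improvement: on nominal days the first scheduled on-drug PT comes after 13 of 14 dosing days, too late for the Table 4 PT guidance to spare more than one active dosing day

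*Combined protocol and SAP*

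**What the plan says.** Section 1.2 states: "The most significant GDC-6599-related finding was a dose-dependent, reversible prolongation of the coagulation parameters aPTT and PT in both rats and monkeys". It also says that the drug "was well tolerated in both rats and cynomolgus monkeys at doses up to 50 mg/kg/day for 4 weeks". For healthy volunteers it reports: "No significant clinical, laboratory, or ECG findings have been observed in the initial six dosing cohorts of the SAD portion", and says the same of three multiple-dose cohorts.

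Table 4 (Section 5.1.3.2) lists "Grade ≥ 3 PT prolongation", defined as PT of at least 1.5 × ULN, and the action is to discontinue study drug. No symptom is required. For an INR above 2 and below 4 it calls for one oral dose of vitamin K and then: "Repeat coagulation parameters daily until INR improves to" below 1.5. The Appendix 10 row "PT, high (not on anticoagulation therapy" also starts Grade 3 at 1.50 × ULN, so the two places agree.

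Appendix 1 marks INR/aPTT/PT at screening, at Visits 2, 4, 5 and 7, and at the follow-up, unscheduled and discontinuation visits. The row "Vitamin K-dependent coagulation factors" has the same treatment visits. Both rows are blank at Visits 3 and 6. The Chemistry row does cover those visits, under footnote h: "Chemistry panel limited to liver function tests (ALP, ALT, AST, total and direct bilirubin". That footnote sets out what to do about raised liver enzymes and says nothing about coagulation.

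**The concern.** The protocol has a laboratory trigger for the drug's main known toxicity, and it acts before any bleeding. A trigger of that kind is useful only if a value arrives while there is still dosing left to stop. Between the baseline sample and the last dosing day, finding a symptom-free PT rise depends on an unscheduled visit. Liver enzymes, by contrast, have a mid-period check with stated actions, from a blood draw that could carry one more tube.

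What is at stake is up to a week of avoidable active dosing in a patient whose PT has already passed the sponsor's own threshold. Section 1.2 says that no patient had received the drug before this trial, and Section 4.1.1.1 admits patients up to age 80.

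**Working it through.** **Inputs**

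- Dosing runs on Days 1–14 and Days 30–43 (Appendix 1, footnote aa).
- Visits 2, 4, 5 and 7 fall on Days 1, 14, 30 and 43. Visits 3 and 6 fall on Days 7 and 36 (Section 4.3.2).
- Assessments on in-clinic dosing days come before the dose unless otherwise specified (Appendix 1, Notes). In-clinic dosing at Visits 2, 4, 5 and 7 is inferred, because that sentence of Section 4.3.2 is partly redacted.
- Coagulation samples go to a central laboratory, the sponsor or a designee (Section 4.5.10). Turnaround is not given; 0 to 3 days is assumed.

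**Period length.** 14 − 1 + 1 = 14 and 43 − 30 + 1 = 14, which reproduces the stated 14 days per period.

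**Dosing before the first scheduled on-drug PT.** 14 − 1 = 13 and 43 − 30 = 13, so 13/14 = 93% of dosing days are complete.

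**Dosing days that can be spared.** Let d be the draw day within the period (Day 36 is period day 36 − 29 = 7). Let k be the number of days until the result is available before that day's dose. Then days spared = max(0, 15 − d − k).

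| Draw | k = 0 | k = 1 | k = 2 | k = 3 |
|---|---|---|---|---|
| Current, Day 14/43 (d = 14) | 1 | 0 | 0 | 0 |
| Added, Day 7/36 (d = 7) | 8 | 7 | 6 | 5 |

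The Day 7/36 dose may be taken at home. A same-day result that arrives after that dose spares 7 days, not 8.

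**Visit windows.** These are not public, so up to 2 days either way is assumed, with k = 1 to 3.

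- Visit 4/7 held 2 days early (d = 12) spares 2, 1 or 0 days; held late, it spares 0. The range is 0 to 2.
- Visit 3/6 spares 9, 8 or 7 days at d = 5 and 5, 4 or 3 days at d = 9. The range is 3 to 9.
- A same-day result at a Visit 4/7 held 2 days early would spare 3 days, which meets the bottom of the second range.

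**Carry-over into Period 2.** A patient with a drug-induced rise on Day 14 was on active drug in Period 1, so Period 2 would be placebo. Stopping then spares no active dosing. A Day 43 result has no later period to act on.

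**Size of the change.** 80 patients × 2 draws = 160 scheduled tests. One patient is 1/30 = 3.3% of a Part A cohort and 1/60 = 1.7% of Part A.

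**The case against.** The strongest reply is that the interval may have been chosen for reasons the public text does not show. The first risk subsection, the dose rationale and several stopping criteria are redacted, and the visible Phase I summary reports no significant laboratory findings. This stands as a limit on confidence; it cannot be shown either to justify the interval or not to.

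Other safeguards exist. Section 4.1.2 excludes PT (INR) or PTT above ULN and bleeding diathesis. Section 4.6.1 has bleeding stops. Section 4.5 makes dosing depend on acceptable local laboratory values. The Internal Monitoring Committee reviews cumulative laboratory data and may recommend changes. These lower the absolute risk. None of them gives a patient's own PT in mid-period: the bleeding stops act after bleeding, the general check schedules no coagulation sample, and the committee sees patterns across patients.

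Three stronger inferences are tempting and should be resisted:

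- A reader might take Table 4 as a binding stop rule that the schedule defeats. Section 5.1.3.2 presents the table as guidance that leaves clinical judgement in charge. The Day 14/43 result can still prompt vitamin K and repeat testing.
- A reader might infer that patients face a serious undetected bleeding hazard. The exclusions, the animal tolerability and the Phase I summary do not support that.
- A reader might count on 5 to 7 days saved. Those figures apply only if PT has crossed 1.5 × ULN by Day 7/36. Table 4's estimate of 4 days for five half-lives implies 0.8 day each, so six days of dosing is about 7.5 half-lives, and exposure should be near steady state under linear kinetics. That describes exposure and does not establish when PT responds.

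**Conclusion.** The point holds as an inexpensive improvement to monitoring. On nominal days, scheduled testing lets a drug-induced PT rise spare at most 1 of 14 active dosing days, and 0 if the result takes a day or more. A mid-period sample would raise that ceiling to about 5 to 7 days at an assumed 1 to 3 day turnaround, provided the threshold has been crossed by then. If PT rises later, the gain could be smaller or zero.

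The conclusion concerns scheduled tests and the Table 4 PT entry only. It rests on nominal visit days and pre-dose sampling. Visit windows, dosing frequency and the redacted safety text could change its size or explain the choice. Confidence is medium, and the change is worth making.

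**What to change.** In Appendix 1, mark INR/aPTT/PT at Visits 3 and 6 on the existing liver-test draw. Extend footnote h to point to the Table 4 coagulation actions. Keep the Day 14/43 samples, which would catch a later effect. Report the results to investigators in the usual way. Sending only values above a threshold would protect the blind better, but it conflicts with the investigator's duty in Section 5.3.5.4 to review all laboratory findings.

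Costs:

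- About 160 scheduled tests and no new scheduled visit. This is not a ceiling, because any INR above 2 and below 4 brings daily repeats.
- Coagulation sample handling where mobile nurses make the Visit 3 or 6 draw.
- A small risk that a mid-period PT rise hints at treatment before the Day 14/43 cough count and the patient-rated severity scores.
- Lost endpoint data. Interruption is not allowed, discontinuation is permanent and patients are not replaced. Each Day 7 stop in an active-first patient therefore loses that patient's whole crossover contrast: 3.3% of a 30-patient cohort, or 1.7% of Part A. A Day 36 stop on active drug keeps the placebo result but loses the Day 43 value needed for the comparison.

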Appendix 1: Schedule of Activities for Part A and Part B

- j Test for FSH may be performed at screening to confirm postmenopausal state, if required per local guidelines.
- k All women of childbearing potential will have a serum pregnancy test at screening. Urine pregnancy tests will be performed at specified subsequent visits. If a urine pregnancy test is positive, it must be confirmed by a serum pregnancy test. On days when both pregnancy test and study drug administration are scheduled, the pregnancy test results must be available prior to dosing.
- l [REDACTED]
- m Urine sample for urinalysis only. Leftover urine sample should not be collected for urine creatinine or biomarkers.
- n COVID-19 testing to be performed as per local regulations or institutional policies.
- o Chest X-ray is to be performed in the following instances:
 - Patients with CRC with asthma or UCC: if no scans have been completed within the last 5 years prior to screening.
 - Patients with CRC with COPD: if no scans have been completed within the last 6 months prior to screening.
- p [REDACTED]
- q On days when multiple PRO assessments are scheduled, the order of questionnaire completion is the following: [REDACTED], VAS, and NRS.
- r VAS will be self-administered once at screening visit via an electronic device at the study site. VAS and NRS will be self-administered daily in the evening during the remainder of screening and treatment periods using a take-home electronic device.
- s The patient is to perform a minimum of three acceptable FVC maneuvers according to the ATS/ERS 2019 guidelines (Graham et al. 2019). The difference between two largest acceptable FVC and FEV₁ measurements must be within 0.15 L (150 mL) variability to meet the repeatability criteria. If there is greater than 0.15 L variability between the three readings, the patient is to perform another FEV₁ measurement. Details on spirometry are provided in Section 4.5.7 and in the pulmonary function and cough monitoring guidance documents. For the screening visits, pre-bronchodilator spirometry should be performed immediately prior to initiating the mannitol challenge test to determine the pre-challenge FEV₁ % predicted value. For subsequent study visits, pre-bronchodilator spirometry should be performed immediately prior to initiating the mannitol challenge test if optional mannitol challenge tests are performed, or should be performed at least 2.5 hours following drug administration.
- t Details on the mannitol challenge test are provided in Section 4.5.5 and in the mannitol challenge test guidance. Medication restrictions prior to the mannitol challenge are provided in Section 4.4.4. If the optional mannitol challenge test is performed at Visit 4 and/or 7, it is to be performed at least 2.5 hours after study drug administration.

